**Observational study on the incidence of infections in patients with relapsed/refractory FLT3+ acute myeloid leukemia treated with Gilteritinib
SEIFEM-GilteRInf 2022 (Gilteritinib Related Infections) Study.**

Background and study rationale

Acute myeloid leukemia (AML) patients with refractory or relapsed (R/R) disease after induction chemotherapy have a poor prognosis with standard chemotherapy [1]. The prognosis may be further aggravated by the susceptibility to infection of this category of patients often due to persistent neutropenia [2][3].

Activating mutations of FMS-like tyrosine kinase 3 (FLT3) are observed in approximately 30 percent of AML cases [4] mainly as in-frame internal tandem duplications (ITDs) within the juxtamembrane region of the protein or as missense point mutations in the tyrosine kinase domain (TKD). FLT3 is expressed in early hematopoietic stem and progenitor cells and regulates their proliferation and differentiation. In patients with AML, the presence of the FLT3 mutation negatively affects survival, both at diagnosis and upon failure of initial therapy [5].

Over the years, several FLT3 inhibitors, currently in development or approved for the treatment of AML, have been devised and vary in kinase selectivity, potency, and clinical activity.

Gilteritinib, is a novel selective tyrosine kinase inhibitor (TKI) that acts by showing greater specificity for FLT3 and higher potency than the first generation of TKIs, competitively inhibits the ATP-binding site of FLT3 receptors, leading to inhibition of receptor signaling and thus cell cycle disruption.

Its approval by the Food and Drug Administration, with indication for FLT3-positive R/R LMA (FLT3+), is based on the results of the phase 3 ADMIRAL study, which demonstrated its superiority over chemotherapy in this setting [6].

In the study, with a median follow-up of 17.8 months, median Overall Survival (OS) was significantly longer (by 3.7 months) in the Gilteritinib arm than in the salvage chemotherapy arm.

OS rates at 12, 18 and 24 months in patients receiving Gilteritinib were 37%, 27% and 20%, respectively (compared with 19%, 15% and 14% in the comparison arm).

Febrile neutropenia was the most common grade ≥ 3 adverse event in the Gilteritinib arm (45.9%), with pneumonia and septic shock the most common fatal adverse events (1.2% and 0.8% of cases, respectively) [7].

In view of recent approval (FDA 2018, EMA 2019), there is a lack of real-life experience in the literature on the management and outcome of infectious issues, which could be significant given the frailty of the patients for whom Gilteritinib is intended.

We also know that Gilteritinib is mainly metabolized through CYP3A4, so there is a recommendation in the data sheet to avoid concomitant use of strong CYP3A4 inducers. The phase I/II CHRYSALIS study [8], which evaluated potential interactions between Gilteritinib and moderate and strong CYP3A4 inhibitors (e.g., some antifungals such as fluconazole, voriconazole, and posaconazole and some antibiotics such as clarithromycin, erythromycin, and azithromycin), demonstrated a less than 2-fold increase in exposure to Gilteritinib with concomitant administration of a strong CYP3A4 inhibitor. However, this increase was not considered

clinically significant because the incidence of AEs did not differ in the two groups.

In a drug-drug interaction study, the effects of moderate CYP3A4 inhibitors (e.g., fluconazole) and strong CYP3A4 inhibitors (e.g., itraconazole) on the pharmacokinetics of Gilteritinib were evaluated.

The results showed that itraconazole was associated with a significant increase in systemic exposure of Gilteritinib (~2.3-fold), while fluconazole was associated with a smaller increase (~1.43-fold) [9]. However, in the ADMIRAL study, the use of posaconazole, itraconazole, and voriconazole was not allowed, and thus the experience of administering these drugs together with Gilteritinib is currently limited [10].

It can be seen from the data sheet that dose reduction of Gilteritinib in case of prophylaxis with azoles is not recommended, but close monitoring of Gilteritinib-related toxicity is recommended [11].

At present, experiences analyzing the incidence of invasive fungal infections in patients on Gilteritinib (25%) [12], whether prophylactically treated or not, are rare.

In light of this evidence, it also becomes essential to evaluate the incidence of side effects related to the use of antibiotic/antifungal/antiviral drugs in the prophylaxis and treatment of infections in the setting of relapsed/refractory patients undergoing continuous therapy such as Gilteritinib.

Study design

The study is observational, retrospective-prospective, multicenter "real-life" study involving 26 centers belonging to the SEIFEM group. Regarding the retrospective part, clinical data will be collected on all patients with LMA FLT3+ (ITD or TKD mutation) treated with Gilteritinib from when the drug was approved and marketed in Italy (April 2, 2020) until April 30, 2022. Enrollment in the prospective cohort will have an estimated duration of 24 months from the time of study approval. Patients enrolled in the last month will be followed for six months from the date of enrollment to check for the occurrence of any infections. For each case of a patient receiving salvage monotherapy with Gilteritinib, a control patient with LMA R/R FLT3+ on salvage chemotherapy should also be included.

Study Duration.

Relative to the prospective part, the study will have a total duration of 24 months from the first patient enrolled and six months of observation from the last patient enrolled.

Population

Inclusion criteria:

- All patients with FLT3+ relapsed/refractory AML to any line of therapy treated with Gilteritinib
- Patients ≥ 18 years of age
- Signature of appropriate informed consent

Exclusion criteria:

- Patients < 18 years old

Study Objectives.

The purpose of the present retrospective/prospective study is to evaluate the "real life" incidence of infectious complications in patients with relapsed/refractory FLT3+ AML treated with Gilteritinib.

Primary objective

To assess "real-life" in patients with relapsed/refractory FLT3+ LMA treated with Gilteritinib the absolute infectious risk and compare it with relapsed/refractory patients receiving chemotherapy.

Secondary objectives.

- To assess the site, incidence and outcome of bacterial/fungal/viral infections in this patient setting
- To assess the need for hospitalization and the duration of hospitalization
- To analyze the different antifungal prophylaxis policies in different Hematology Centers and correlate them with the incidence of infection
- To analyze the incidence of side effects related to the use, in combination with Gilteritinib, of antifungal/antibacterial/antiviral drugs (in prophylaxis/therapy).

Methods

The proposed study is retrospective-prospective, multicenter, observational.

Data will be retrospectively collected from all cases observed from April 2, 2020 until April 30, 2022 about the infectious event and related treatment information (database attached).

In the prospective cohort, enrollment will have an estimated duration of 24 months from the time of study approval. Patients enrolled in the last month will be followed for six months thereafter to check for the occurrence of any infections.

Data from patients with gilteritinib monotherapy and data from patients for whom the clinician's choice is the use of chemotherapy (consisting, for example, of the following regimens: FLA-IDA, MICE, MEC, intermediate/high-dose cytarabine) will have to be analyzed to assess the infectious risk associated with gilteritinib monotherapy.

It is reiterated that since this is an observational study, the choice of therapy is at the discretion of the treating hematologist and independent of enrollment in this study.

Informed consent will be sought from all patients still alive at the time of initiation of data collection and from patients whose data will be collected prospectively. However, it should be noted that since this is a study that mainly considers patients with relapsing hemopathies that could be complicated by life-threatening infections, the rate of obtainable consents may be reduced due to the mortality of these hemopathies.

The incidence of infection will be related to the following variables:

- Age
- Sex
- Comorbidities
- Type of antimicrobial prophylaxis performed
- Type of FLT3 mutation (ITD vs TKD)
- Type of response to treatment
- Hospitalization and duration

Any side effects related to the combination of Gilteritinib with antimicrobial drugs used in prophylaxis/therapy by different centers will also be evaluated.

The study will not affect normal care practice in any way, as there is no blood sampling for patients. Each patient and each control will be assigned an identification code that will allow the omission of any reference that would allow patient recognition.

Clinical information will pertain to the coordinating center and will be collected within a database.

Based on the following considerations:

- it is assumed that the reference population, or target population from which the sample is drawn (78 patients), is Gaussian distributed with unknown variance;
- the null hypothesis (superposibility of the two populations: sample and target) is rejected if the sample mean differs from the mean value of the reference population by an amount, in absolute value, equal to or greater than 36.7 percent of the standard deviation;

- we adopt, for testing the hypotheses (null and alternative), the two-tailed Gauss z-test with $\alpha = 0.05$ (error of the first kind) and $\beta = 0.10$ (error of the second kind), which implies, as is well known, a test power of 90%;

at least 78 patients are expected to be enrolled.

The analysis will be aimed at evaluating the distribution of infectious events (viral/bacterial/fungal) and identifying parameters that significantly influence the outcome of infectious complication.

With regard to descriptive statistical analyses, central tendency, variability, symmetry and kurtosis will be calculated, all accompanied by appropriate graphical representations; with regard to inferential analyses, in addition to multivariate binary logistic regression, parametric and nonparametric hypothesis testing will be carried out, respectively, for quantitative variables with parametric tests such as: Student's t-test, Fisher's F-test, etc. and for categorical variables by nonparametric tests such as: chi-square, Mann Whitney's U, Fisher's exact test, etc. Only results with p-values ≤ 0.05 will be considered statistically significant.

The study does not involve any expenses related to data collection or additional examinations.

Italian Hematology Centers belonging to the SEIFEM Group, which includes both university and hospital facilities, will participate in the study (Appendix 1: list of participating centers).

Data collection and analysis and report preparation will be the responsibility of the scientific board.

Dissemination of results

Publication of results in leading international scientific journals dealing with topics related to hematology and infectious diseases. Also, presentation of results at major national and international hematology congresses, (American Society of Hematology, European Hematology Association, Italian Society of Hematology)

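### The inclusion list admits only gilteritinib-treated patients, and no rule says how the chemotherapy controls required by the primary comparison are chosen

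*Combined protocol and SAP*

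**What the plan says.** - **Population, Inclusion criteria.** There are three items: "All patients with FLT3+ relapsed/refractory AML to any line of therapy treated with Gilteritinib", age 18 or over, and signed consent. The only exclusion is age under 18. Chemotherapy is not mentioned.
- **Study design.** For the retrospective part, "clinical data will be collected on all patients with LMA FLT3+ (ITD or TKD mutation) treated with Gilteritinib" between 2 April 2020 and 30 April 2022. For each gilteritinib monotherapy case, "a control patient with LMA R/R FLT3+ on salvage chemotherapy should also be included" (LMA is AML).
- **Primary objective.** Estimate the absolute infectious risk under gilteritinib and "compare it with relapsed/refractory patients receiving chemotherapy". FLT3 status is not restated for the comparator.
- **Methods.** "Data will be retrospectively collected from all cases observed from April 2, 2020 until April 30, 2022". The analysis uses gilteritinib monotherapy patients and "data from patients for whom the clinician's choice is the use of chemotherapy", with example regimens. Prospective enrolment lasts 24 months and is stated for the whole cohort.
- **Methods, sample size.** "the null hypothesis (superposibility of the two populations: sample and target) is rejected" at a stated distance in standard deviations, and "at least 78 patients are expected to be enrolled".
- **Consent.** The inclusion list asks for a signature without exception. Methods seeks consent from patients alive when data collection starts and from prospective patients, and expects deaths to reduce the number obtained.

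**The concern.** The eligibility list contradicts the design, the primary objective and the planned analysis, because it leaves out the comparator that all three need.

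The more serious gap lies behind that mismatch. The two groups are sampled differently. Gilteritinib patients are all taken, which leaves a center little choice. A control is one patient per case, with no order, index date, center rule or matching factor stated. In the retrospective part a control's infections are already in the chart when it is picked. If infected patients are more likely, or less likely, to be picked than uninfected ones, the control incidence moves and the comparison shows a difference that is not there. Centers following the same text could also build different control groups. The comparative half of the primary objective is at stake; the absolute-risk estimate for gilteritinib is not affected.

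**Working it through.** **1. Does the sample size define the comparator?** Inputs from Methods: 0.367 SD, two-sided alpha 0.05, power 90%. One-sample z-test: n = ((1.960 + 1.282)/0.367)² = 78.0. The planned 78 reproduces, but as a test of one sample against a reference population. It contains no control group and no allocation ratio, and the text does not say whether 78 counts controls. Both readings are carried below: 39 per group (78 in total) and 78 per group (78 cases plus 78 controls).

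**2. Do the stated dates cover controls?** The Study design dates are worded for gilteritinib-treated patients. The Methods sentence covers all cases. The Study design section sets case against control, but the Background uses the word for AML cases in general. The retrospective control window is therefore ambiguous. The prospective period applies to both groups.

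**3. Effect of selection on infection status.** Assumed, not in the documents: s, the chance that an infected eligible chemotherapy patient is picked divided by the chance for an uninfected one, with range 0.67 to 1.5. The true incidence p is the same in both groups; 50% and 25% are shown. The incidence among picked controls is q = ps/(ps + 1 − p). For p = 0.5 and s = 1.5, q = 0.75/1.25 = 60.0%.

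**4. Limit this to the retrospective part.** From 2 April 2020 to 30 April 2022 is 24.9 months; prospective enrolment is 24 months. At a constant monthly rate (assumed), the retrospective share is w = 24.9/48.9 = 0.509. With s = 1 prospectively, the control incidence is q* = wq + (1 − w)p. For p = 0.5 and s = 1.5, q* = 0.509 × 0.600 + 0.491 × 0.500 = 55.1%.

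**5. Chance of a false p ≤ 0.05.** Two-sided pooled z-test of two proportions, unadjusted. Example: p = 0.5, s = 1.5, 39 per group, shift 0.0509, null SE 0.1131, actual SE 0.1129. The chance is Φ((0.0509 − 1.960 × 0.1131)/0.1129) + Φ((−0.0509 − 1.960 × 0.1131)/0.1129) = 0.065 + 0.008 = 7.3%.

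Differences are gilteritinib minus chemotherapy, in percentage points.

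| Selection affects | p | s | Control incidence | False difference | 39 per group | 78 per group |
|---|---|---|---|---|---|---|
| Retrospective part only | 50% | 0.67 | 45.0% | +5.0 | 7.3% | 9.6% |
| | 50% | 1.5 | 55.1% | −5.1 | 7.3% | 9.7% |
| | 25% | 0.67 | 21.6% | +3.4 | 6.5% | 8.0% |
| | 25% | 1.5 | 29.2% | −4.2 | 7.0% | 9.1% |
| All controls | 50% | 0.67 | 40.1% | +9.9 | 14.0% | 23.5% |
| | 50% | 1.5 | 60.0% | −10.0 | 14.3% | 24.0% |
| | 25% | 0.67 | 18.3% | +6.7 | 11.1% | 17.5% |
| | 25% | 1.5 | 33.3% | −8.3 | 12.7% | 20.7% |
| Either | any | 1 | p | 0 | 5% | 5% |

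**6. Does the planned regression help?** From step 3, the odds of infection among selected controls are ps/(1 − p), that is, s times the true odds. If s is the same at every level of age, sex, comorbidity and the other listed variables, the odds are multiplied by s within each level as well. Adjusting for those variables does not remove it.

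**The case against.** The controls are not undefined. The Study design and Methods sections give disease, mutation, treatment type, ratio and example regimens, so the mismatch with the list is largely a drafting fault that a sensible center would read past. This stands, and it narrows the substantive gap to the selection rule and the retrospective window.

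Nothing in the documents supports any value of s other than 1. Seventy-eight patients over 26 centers is three per center. A center with few FLT3+ chemotherapy patients would have to take them all and would have no choice to exercise. This also stands: the documents give no count of available controls, so selection is possible but not shown. It does not settle the window, because a center short of controls could look outside the stated dates.

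A reader might infer a false difference of 10 points and a false-positive rate of up to 24%. That needs outcome-related selection of every control. Prospective controls chosen at treatment start have no infection record yet, so selection there could work only through baseline risk. The larger figures are an upper case.

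A reader might also infer that the signed-consent item removes retrospective patients who have died. Methods points the other way: it seeks consent only from living and prospective patients and foresees losses through mortality. No sentence says outright that the deceased are included, so this is a clarification and not a demonstrated bias.

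**Conclusion.** The point holds as a contradiction within the protocol plus a missing selection rule. The list excludes the comparator that the primary objective needs, and the text permits retrospective controls to be chosen with their outcome known.

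With s between 0.67 and 1.5 in the retrospective half only, constant monthly accrual and an unadjusted test, the false difference is about 5 points at a true 50% incidence and 3.4 to 4.2 points at 25%. The false-positive chance is about 7% (39 per group) or 8% to 10% (78 per group). If some baseline-risk selection also occurs prospectively, the result lies between these figures and the all-controls rows. At s = 1, or where every eligible patient must be taken, there is no bias. The documents fix neither the size of s nor its direction, so they do not support saying that the comparison will favor either treatment.

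The change should be made. Confidence is high on the mismatch and the missing rule; the size is illustrative.

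**What to change.** Reconcile the passages by amending the Population section.

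1. Keep the gilteritinib criterion for cases and add one for controls: adults with FLT3+ relapsed/refractory AML given salvage chemotherapy, at the same centers, within the same retrospective dates and prospective enrolment period as the cases.
2. State a non-discretionary selection rule applied without regard to infections. Either take all eligible chemotherapy patients in the window, or take the not-yet-used eligible patient at that center whose chemotherapy start is nearest to the case's start within the window. The first option replaces the 1:1 ratio, and the Study design text would have to say so.
3. Use each control once. Keep a case without a control for the absolute-risk estimate only. State in advance to which group a patient who receives both treatments is assigned.
4. Minor: align the signed-consent item with Methods, and state whether deceased retrospective patients are included, subject to ethics committee approval.

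The cost is a protocol amendment with ethics review and a simple screening log at each of the 26 centers. A fixed window and rule may leave fewer controls; how many cannot be judged from the documents. Patient care does not change.

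### The inclusion list requires a consent signature without exception, while Methods plans none for retrospective patients already dead; the plan should state whether they are kept

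*Combined protocol and SAP*

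**What the plan says.** All references are to the combined protocol and SAP.

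- **Population, inclusion criteria:** "Signature of appropriate informed consent". No exception follows. The only exclusion criterion is age under 18.
- **Study design,** on the retrospective part: "clinical data will be collected on all patients with LMA FLT3+ (ITD or TKD mutation) treated with Gilteritinib", from Italian marketing (April 2, 2020) to April 30, 2022.
- **Methods,** same window: "Data will be retrospectively collected from all cases observed from April 2, 2020 until April 30, 2022".
- **Methods,** on consent: "Informed consent will be sought from all patients still alive at the time of initiation of data collection". The same sentence adds the prospective patients. The next sentence warns that "the rate of obtainable consents may be reduced due to the mortality of these hemopathies", and no rule for unsigned patients follows.
- **Secondary objectives:** "To assess the site, incidence and outcome of bacterial/fungal/viral infections in this patient setting".

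The public text does not include the consent pages, and the attached database is not reproduced.

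**The concern.** A gilteritinib patient treated in the retrospective window who died before data collection began belongs to the cohort as Study design and Methods describe it. The same patient fails the signature criterion, and Methods plans no step by which a signature could be obtained. No visible sentence says which statement governs.

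Centers screen against the inclusion list, and 26 of them must apply it in the same way. Where the list is applied literally, two things follow for the retrospective part:

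- Patients are selected on having survived until data collection, in a disease with high early mortality.
- Every infection that was fatal before that date disappears from the secondary objective on infection outcome. This needs no assumption about how infection and death are related.

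If some centers apply the list literally and others do not, the retrospective cohort becomes a mixture whose composition cannot be reconstructed without counts.

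**Working it through.** **Reading the text.** The plan gives no figure on this point, so there is none to reproduce. Its sample size of 78 does not depend on the consent rule.

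| Patient | Within the described cohort? | Consent sought under Methods? | Meets the signature criterion as written? |
|---|---|---|---|
| Prospective | Yes | Yes | Yes, if signed |
| Retrospective, alive at initiation | Yes | Yes | Yes, if signed |
| Retrospective, already dead | Yes | No | No |
| Retrospective, alive at initiation, dies or is untraceable before signing | Yes | Planned, not obtained | No |

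The last two rows are the gap.

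**Illustration of size, literal reading only.**

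Inputs from Background and study rationale: survival at 12, 18 and 24 months of 37%, 27% and 20% on gilteritinib, and 19%, 15% and 14% on chemotherapy. The retrospective window is about 25 months (Study design).

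Assumptions, none of them in the documents:

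- The trial survival rates apply to these patients.
- Survival S(t) is log-linear between the quoted points, starting from 100% at month 0, with the last slope continued after month 24.
- Data collection starts L = 0 or 6 months after April 2022.
- Treatment starts are even over the window, rise linearly from zero, or fall linearly to zero.

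With u = months before the end of the window (0 to 25), the share dead before data collection is

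D = 1 − ∫ w(u) S(u + L) du,

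where w(u) = 1/25 (even), 2(25 − u)/625 (rising) or 2u/625 (falling).

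Worked case, gilteritinib, even starts, L = 0. The area under S by segment is:

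- months 0-12: (1 − 0.37)·12 / ln(1/0.37) = 7.604
- months 12-18: (0.37 − 0.27)·6 / ln(0.37/0.27) = 1.904
- months 18-24: (0.27 − 0.20)·6 / ln(0.27/0.20) = 1.400
- months 24-25: 0.195

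The sum is 11.103. Then 11.103/25 = 0.444, so D = 0.556.

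| Starts | Gilteritinib, L = 0 | Gilteritinib, L = 6 | Chemotherapy, L = 0 | Chemotherapy, L = 6 |
|---|---|---|---|---|
| Rising | 0.433 | 0.637 | 0.570 | 0.782 |
| Even | 0.556 | 0.706 | 0.685 | 0.816 |
| Falling | 0.679 | 0.774 | 0.800 | 0.850 |

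The even value must be the average of the rising and falling values: (0.433 + 0.679)/2 = 0.556. Holding survival flat after month 24 lowers no entry by more than 0.016.

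The ranges are therefore 43-77% for gilteritinib and 57-85% for chemotherapy. The chemotherapy columns also assume that controls come from the same window, which the plan does not state.

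**What these figures are not.** They are all-cause deaths, not bias in infection risk. By Bayes' rule, infection incidence among survivors is below the full-cohort incidence if infected patients die more often, equal to it if there is no association, and above it if infected patients die less often (for instance because longer survivors have more time in which to become infected). The documents do not say which applies.

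**The case against.** The strongest reply is that the intent is largely visible. The retrospective part is described twice as complete. Asking for consent only from those still living makes most sense if the dead enter without a signature. Lack of consent is not an exclusion criterion, and the criterion itself speaks of consent that is appropriate. A waiver for deceased patients would naturally sit in the consent pages, which are not in the public text, so its absence there cannot be held against the plan.

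Most of this stands. Inclusion of the deceased is the likelier intent, and it cannot be said that no rule exists anywhere. What remains is that the criterion and the Methods text disagree as written. The remark about fewer obtainable consents does not reconcile them: it can mean fewer signatures with the patients kept, or fewer patients.

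The reply is also right about the numbers. They depend on an accrual pattern, a lag and trial survival rates that are assumed, and they apply to the less likely reading. The share of patients in the retrospective part is not stated.

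A reader might go further and infer that the study will be a survivors-only sample, or that its infection risk will be underestimated. The documents support neither. Nothing shows that any center would apply the criterion literally, prospective patients are outside the problem, and the direction for overall incidence is open.

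**Conclusion.** The point holds as a low-severity inconsistency. An unqualified eligibility rule conflicts with the stated retrospective cohort. Applied as written, it would select that cohort on survival and remove infections fatal before data collection from the outcome objective.

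Under the literal reading and the assumptions above, roughly 43-77% of retrospective gilteritinib patients would be lost. If controls came from the same window, about 57-85% of them would be lost, so the loss could differ between the groups that the primary objective compares. These ranges illustrate what is at stake. They are neither a forecast nor a bound, and they do not measure bias in infection incidence.

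The finding rests on the visible text. A rule in the consent pages or the database attachment would reduce it to a cross-reference.

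**What to change.** Reconcile the inclusion criterion with Methods:

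1. Limit the signature requirement to patients alive at initiation of data collection and to prospective patients.
2. State that retrospective patients already deceased at that date are included on the basis the ethics approval allows. The sponsor needs to confirm that basis.
3. State how patients alive at initiation who die or cannot be traced before signing are handled.
4. Apply the same rule to gilteritinib cases and chemotherapy controls.
5. Report, per group, the numbers alive and consented, alive and not consented, and deceased.

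The cost is a few lines in the eligibility and Methods sections, confirmation of the ethics position, and three counts per group from the centers. No new procedures are needed. If deceased patients were always meant to be included, the wording records that intent and the counts let readers check that the retrospective cohort is complete.

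### The objective on centres' antifungal prophylaxis policies has no policy or centre variable behind it; the only specified contrast is prophylaxis received, which is open to confounding by indication

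*Combined protocol and SAP*

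**What the plan says.** The combined protocol and SAP lists, under Secondary objectives, "To analyze the different antifungal prophylaxis policies in different Hematology Centers and correlate them with the incidence of infection".

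Methods introduces its list of explanatory variables with "The incidence of infection will be related to the following variables" and gives seven: age, sex, comorbidities, prophylaxis, FLT3 mutation type, response, and hospitalization with its duration. The prophylaxis item is "Type of antimicrobial prophylaxis performed". Neither the centre nor its policy is in the list.

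Centres' use of prophylactic drugs comes up once in Methods, in connection with toxicity and not infection: "Any side effects related to the combination of Gilteritinib with antimicrobial drugs used in prophylaxis/therapy by different centers will also be evaluated".

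On treatment allocation, Methods states that "the choice of therapy is at the discretion of the treating hematologist and independent of enrollment in this study". On modelling it says only that "in addition to multivariate binary logistic regression, parametric and nonparametric hypothesis testing will be carried out". No covariates, centre term or method for clustering is given.

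**The concern.** The objective and the analysis have different exposures. A centre's policy depends on where a patient is treated. Prophylaxis performed depends on what a clinician decided for that patient, and it covers all antimicrobials, not antifungals alone.

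An individual decision can track the patient's risk of infection. A patient with an earlier fungal infection is a likely candidate for secondary prophylaxis, and is also at higher risk of another infection. The Background gives a second influence on choice: itraconazole raised gilteritinib exposure about 2.3-fold, the phase 3 trial did not allow three azoles, and monitoring for toxicity is advised.

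Of the listed variables, age, sex and comorbidities could adjust in part for such choices. Response and hospitalization arise after treatment starts, so they are not suitable for that purpose. Prior fungal infection, neutropenia and prior lines of therapy are not named.

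At stake is whether the study can answer this secondary objective at all, and whether a table of infection by prophylaxis received would be misread as showing what prophylaxis achieves. The primary objective is not affected.

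**Working it through.** **1. The plan's own figure.** The plan gives no sample size for this objective. Its only one is 78 patients, from a two-sided z-test with α = 0.05, β = 0.10 and a shift of 0.367 SD. As a one-sample test this reproduces: n = ((1.960 + 1.282)/0.367)² = 78.01. It concerns a single mean against a reference value, so it says nothing about prophylaxis.

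**2. Objective and Methods side by side.**

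| | Secondary objective | Methods |
|---|---|---|
| Exposure | Centre's policy | Prophylaxis the patient received |
| Drug class | Antifungal | Any antimicrobial |
| Level | Centre | Patient |
| Centre or policy recorded | Needed | Not a named variable |

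**3. How far confounding could move the received-prophylaxis contrast.** All inputs are assumptions; the documents supply none. A share h = 0.1 to 0.3 of patients has a prior fungal infection carrying k = 2 to 4 times the risk. Prophylaxis is given to 95% of them and 50% of the others. The true risk ratio is 0.50. In units of the risk of an untreated patient without prior infection:

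- Treated: T = 0.5 × [0.95hk + 0.50(1−h)] / [0.95h + 0.50(1−h)]
- Untreated: U = [0.05hk + 0.50(1−h)] / [0.05h + 0.50(1−h)]
- Apparent crude risk ratio = T/U

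For h = 0.1, k = 2: T = 0.5 × 0.640/0.545 = 0.587 and U = 0.460/0.455 = 1.011, so T/U = 0.58.

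For h = 0.3, k = 4: T = 0.5 × 1.490/0.635 = 1.173 and U = 0.410/0.365 = 1.123, so T/U = 1.04.

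| | k = 2 | k = 3 | k = 4 |
|---|---|---|---|
| h = 0.1 | 0.58 | 0.66 | 0.74 |
| h = 0.2 | 0.65 | 0.78 | 0.92 |
| h = 0.3 | 0.70 | 0.88 | 1.04 |

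Every cell understates the benefit. Only one of nine exceeds 1.

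**4. A second illustration, with no true effect.** Assume half the patients are high-risk, with 1.5 to 3 times the risk of the rest. Overall incidence is 25%, borrowed from the invasive fungal infection figure in the Background. Prophylaxis goes to 60–80% of high-risk and 40% of low-risk patients.

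- Mildest case: risks are 0.20 and 0.30. Treated (0.5×0.6×0.30 + 0.5×0.4×0.20)/0.50 = 0.26; untreated (0.5×0.4×0.30 + 0.5×0.6×0.20)/0.50 = 0.24; odds ratio 1.11.
- Strongest case: risks are 0.125 and 0.375. Treated (0.5×0.8×0.375 + 0.5×0.4×0.125)/0.60 = 0.292; untreated (0.5×0.2×0.375 + 0.5×0.6×0.125)/0.40 = 0.1875; odds ratio 1.78.

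**5. Direction.** Steps 3 and 4 both assume that higher-risk patients are treated more often. If interaction concern led to azoles being withheld from higher-risk patients, those patients would be over-represented among the untreated, and the apparent risk ratio would fall below the true one. The sign is not fixed.

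**6. What a policy contrast could show.** 78/26 = 3 patients per centre, or 156/26 = 6 if one control per case is additional. Assume two policies, 13 centres each, and an intraclass correlation (ICC) of 0 to 0.10. The design effect is 1 + (m−1)×ICC for m patients per centre. At ICC 0.10 the effective size per group is 39/1.2 = 32.5, or 78/1.5 = 52.

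| Total patients | Power, 25% vs 12.5% | Power, 25% vs 10% |
|---|---|---|
| 78 | 29% (ICC 0) to 25% (ICC 0.10) | 41% to 35% |
| 156 | 52% to 37% | 70% to 52% |

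Non-adherence dilutes the contrast as well. If uptake were 80% under one policy and 20% under the other, a true risk ratio of 0.50 would appear as (0.8×0.5 + 0.2)/(0.2×0.5 + 0.8) = 0.60/0.90 = 0.67. With 25% risk in untreated patients that is 15% against 22.5%, and power at 39 per group is about 13% before any clustering.

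**The case against.** **Policy may mean practice.** In an observational study of routine care, a centre's policy can be read as what it usually gives, and prophylaxis performed, tabulated by centre, would then come close to the objective. This stands in part, and the fix accepts usual practice where nothing is written down. Even so, the plan names no centre variable and no such tabulation for infection.

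**The data may already exist.** Methods refers to an attached database that is not in the documents. It may hold centre, policy or prior-infection fields, and comorbidities is undefined and could include prior fungal infection. This stands: a reader might infer that the study cannot separate primary from secondary prophylaxis, but the documents show only that no named variable does so. A field would still not supply a definition of policy or an analysis.

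**Adjustment is planned.** The illustrations are crude, whereas logistic regression is foreseen. It could remove some of the bias. How much cannot be judged, because its covariates are not stated.

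**The policy contrast has its own problems.** A reader might infer that it would be free of bias. It avoids patient-level indication, but Methods says that participating centres include university and hospital facilities, so case mix may differ, and power is low. This stands in full. It is a reason to report estimates with intervals as exploratory, and does not make prophylaxis received an answer to a question about policy.

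**The objective is modest.** It is one of four secondary objectives and speaks of correlation, not effect. That limits the severity. It does not supply the missing exposure.

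**Conclusion.** The concern holds in a limited form. The policy objective has no stated operational variable, and the only contrast specified between prophylaxis and infection uses what each patient received, with no named variable for centre, policy or prior fungal infection. That contrast is open to confounding by indication.

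Two stronger readings are not supported. A reader might infer that the plan has replaced the policy objective with the patient-level comparison; the documents never withdraw the objective or say that the variable list is meant to answer it. A reader might also infer that effective prophylaxis will look useless or harmful. The range of 0.58 to 1.04 for a true risk ratio of 0.50 rests wholly on assumed prevalence, risk and uptake, its midpoint is 0.78, and only the extreme corner passes 1. With interaction concern able to act either way, neither size nor direction can be stated for this study.

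The change is worth making because it is cheap, lets the study address its own objective, and reduces a foreseeable bias in the received-prophylaxis analysis.

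**What to change.** - **Record policy.** Obtain from each of the 26 centres its antifungal prophylaxis policy for the patients in this analysis, or its usual practice if there is no written policy, with dates of any change. Dates matter because inclusion starts in April 2020 and continues through a 24-month prospective phase. Complete this before outcomes are analysed.
- **Analyse policy.** Assign each patient the policy in force at treatment start, whatever was actually given. Report infection incidence by policy with confidence intervals, accounting for clustering by centre, and label the analysis exploratory.
- **Record prior infection.** Add a field for prior proven or probable fungal infection, unless the database already has one.
- **Keep prophylaxis received as a separate analysis.** Restrict it to primary prophylaxis or stratify it by prior fungal infection.

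The cost is one short form per centre and one data field; patient care is unchanged. The policy contrast will be diluted where centres depart from their policy, will have low power at about 3 to 6 patients per centre, and will remain subject to case-mix differences between centres. The report should say so.
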